6. CLINICAL STUDY POPULATION

6.1. Inclusion Criteria

Subjects must meet all of the following inclusion criteria to be eligible for participation in this study:

1. Male or female subject ≥ 18 and < 65 years of age, on the date of signing the ICF.
2. A body mass index (BMI) between 18–32 kg/m², inclusive.
3. Diagnosis of RA ≥ 6 months prior to screening AND meeting the 2010 ACR/EULAR criteria of RA AND ACR functional class I-III.
4. Have ≥ 6 swollen joints (from a SJC66) AND ≥ 8 tender joints (from a TJC68) at screening and at the baseline visit (Visit 1) prior to the first IP dosing.
5. DAS28 (CRP) > 3.2 (moderate disease) at screening.
6. Screening serum high sensitivity CRP (hsCRP) $>$ upper limit of normal (ULN, central laboratory reference: ≤ 5.0 mg/L).
7. Inadequate response to MTX, i.e. treatment-experienced subjects who demonstrated inadequate clinical response during treatment with MTX.
8. Have received MTX for ≥ 6 months and on stable dose (10 to 20 mg/week) of MTX for at least 4 weeks prior to screening and willing to continue on their current stable dose and dosing regimen for the duration of the study.
9. If taking systemic steroids, prednisone equivalent at a dose of ≤ 10 mg/day and stable for at least 4 weeks prior to the first IP dosing.
10. If taking non-steroidal anti-inflammatory drugs (NSAIDs), these must be at a stable dose for at least 2 weeks prior to first IP dosing.
11. Female subjects of childbearing potential must have a negative highly sensitive (serum beta human chorionic gonadotropin) pregnancy test at screening. Female subjects of non-

childbearing potential must have a negative FSH test at screening or must be at least 6 months permanently surgically sterile (bilateral oophorectomy, i.e. surgical removal of ovaries, bilateral salpingectomy or hysterectomy, i.e. surgical removal of uterus).

12. Female subject of child bearing potential or male subject must agree to use highly effective contraception/preventive exposure measures (as described in Section 6.3.1).
13. Able and willing to comply with the CSP requirements (e.g. opening and reconstituting the IP formulation) and must sign and date the ICF as approved by the Independent Ethics Committee (IEC) / Institutional Review Board (IRB), prior to any screening evaluations.
14. Able and willing to comply with restrictions on prior and concomitant medication as described in Section 6.3.2.

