6.5.2. Blinding and Unblinding

This is a randomized, double-blind clinical study. The subjects and the entire clinical study team, including the investigators, clinical study coordinators, and sponsor personnel are blinded to treatment assignment.

Blinded and packaged medication will be provided to the site. All IP formulations will be identical in appearance, shape, smell and taste, and will be packaged in the proper proportion to assure desired dosages and maintenance of the blinding.

The blind can be broken by the investigator for the safety of a subject. The investigator is encouraged to discuss considerations to break the blind with the sponsor's medical responsible, whenever possible and where the situation allows. However, the responsibility to break the treatment code in emergency situations resides solely with the investigator. The investigator is not required to discuss unblinding beforehand if he or she feels rapid emergency unblinding is necessary, but is required to inform the sponsor within 24 hours after unblinding has occurred.

The blind can be broken via IXRS by the investigator.

If the blind is broken for any reason during the course of the clinical study, the moment on which the blind was broken and all other relevant information will be documented by the site. The reason for breaking the blind will be indicated and justified in the source documentation.

If an AE leads to unblinding, the AE will be given as the reason for unblinding. All subjects who are unblinded should, where possible, complete the FU visit assessments 14±3 days after unblinding. Any AEs will be followed until resolution.

Code-breaking information (via IXRS vendor) will be provided to the bioanalytical laboratory responsible for plasma drug determination sample analysis, the person responsible for providing unblinded data to the Data Safety Monitoring Committee, the contract research organization (CRO) responsible for the population PK modeling, and to the sponsor pharmacovigilance vendor for SAE reporting purposes.

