8.4. Efficacy Assessments

8.4.1. Joint Counts

On the visits specified in the Schedule of Activities in Section 8.11 (see also Section 8.1, “Timing of Assessments”), each of 68 joints will be evaluated for tenderness (tender joint count, TJC68), and each of 66 joints will be evaluated for swelling (swollen joint count, SJC66) (Appendix 9).

A joint assessor with adequate training and experience in performing joint assessments will be designated at each study site to perform all joint assessments. The joint assessor should preferably be a rheumatologist, however, if a rheumatologist is not available, it should be a health care worker with at least one year’s experience in performing joint assessments. The assessor should remain the same throughout the study per subject, as much as possible. It is required that the designated joint assessor identifies an appropriate back-up assessor to provide coverage if the designated joint assessor is absent.

8.4.2. [REDACTED]

[REDACTED]

[REDACTED]

[REDACTED]

8.4.2.1. [REDACTED]

[REDACTED]

[REDACTED]

[REDACTED]

[REDACTED]

[REDACTED]

8.4.2.2. [REDACTED]

[REDACTED]

[REDACTED]

[REDACTED]

[REDACTED]

[REDACTED]

8.4.3. [REDACTED]

[REDACTED]

[REDACTED]

[REDACTED]

[REDACTED]

[REDACTED]

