8.5.2. Clinical Laboratory Evaluations

The following clinical laboratory safety tests will be performed:

- **Hematology:** hematocrit, hemoglobin, red blood cell count, white blood cell count, white blood cell differential count (absolute and relative), mean corpuscular volume (MCV), mean corpuscular hemoglobin (MCH), mean corpuscular hemoglobin concentration (MCHC), red blood cell distribution width and platelets.
- **Coagulation:** INR (only when increase in LFTs, see Section 6.4), activated partial thromboplastin time and prothrombin time.
- **Clinical chemistry:** glucose, urea, creatinine, uric acid, sodium, potassium, calcium, reflex calcium (free/ionized; only if serum calcium total is elevated), chloride, phosphorus, AST, ALT, GGT, total bilirubin, alkaline phosphatase (ALP, ALP fractions only if ALP is elevated), creatine phosphokinase, lipase, amylase, lactate dehydrogenase, insulin, hemoglobin A1c (HbA1c), albumin, total proteins, triglycerides, cholesterol, high-density lipoprotein (HDL), low-density lipoprotein (LDL), and hsCRP. Homeostatic model assessment of insulin resistance (HOMA-IR, see [Definition of Terms](#)) and HDL/LDL ratio will be derived from clinical chemistry parameters. An estimate of the

ClCr based on the serum creatinine level will be calculated by the central laboratory using the Cockcroft-Gault formula (see [Definition of Terms](#)).

– **Urinalysis:**

Dipstick: pH, glucose, proteins (qualitative), blood, leukocytes, ketones.

Microscopic examination of the sediment for cellular elements (cylinders, erythrocytes, leukocytes), if indicated (when the test strip was positive for blood and/or proteins).

Quantitative urine proteins, only when the test strip was positive for proteins.

Calcium, phosphate, creatinine and N-acetyl- β -D-glucosaminidase (NAG). The urine protein to creatinine ratio will be derived.

– **Serology:**

HBsAg and hepatitis C antibody, and HIV 1 and 2 (at screening). Positive hepatitis and HIV results should be reported by the investigator as required by local law.

– FSH test for females at screening to confirm menopause if applicable

– **Pregnancy test for females:**

serum beta human chorionic gonadotropin at screening, baseline (Visit 1), at Visit 4 (Day 29) and at Visit 5 (Day 43), , or the ED visit, if applicable (all female subjects).

– **QuantiFERON-TB Gold test** to check for latent or active TB (at screening). TB results should be reported by the investigator as required by local law.

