– **SARS-CoV-2:**

RT-PCR from a nasal swab sample to check for SARS-CoV-2 infection at screening and RT-PCR from a nasal swab sample and serology testing at baseline, and throughout the study as needed (when SARS-CoV-2 symptoms present).

The clinical laboratory evaluations will be performed at visits specified in the Schedule of Activities in Section 8.11 (see also Section 8.1, “[Timing of Assessments](#)”). Reference ranges will be supplied by the central laboratory. Clinical laboratory values outside the normal range will be flagged and clinical relevance will be assessed by the investigator. Only laboratory test abnormalities judged as clinically significant by the principal investigator should be recorded as AEs.

The details of blood and urine sample handling and shipment instructions will be provided in a separate laboratory manual.

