8.11. Schedule of Activities

For detailed instructions on the clinical study procedures, please see referred sections and Section 8.1, “[Timing of Assessments](#)”.

EVENT	SCREENING PERIOD	TREATMENT PERIOD ^{1,2}						FOLLOW-UP PERIOD ²
		1	2	3	4	5	ED ³	
Study visit	S	1						FU Visit
Study Weeks		Baseline	1	2	4	6		
Study Day (D) ± Days	-21 to -1	1	8 ± 2	15 ± 2	29 ± 2	43 ± 2	Early treatment discontinuation	57 ± 3
On site visit	✓	✓		✓	✓	✓	✓	✓
Telephone call			✓					
Informed consent	✓							
Inclusion/exclusion criteria	✓	✓						
Demographics	✓							
Medical history	✓							
FSH test (postmenopausal women)	✓							

¹ On dosing days, all assessments are to be performed within 3 hours pre-dose, unless otherwise specified.

² Subjects must come for the study visits 1, 3 and 5 in the morning in a fasting state (no food intake for at least 8 hours). For Visit 1 (predose measurements) and for 2 post dose visits (Visit 3, 4 or 5) all attempts should be made to plan the visit within 2 days following MTX intake.

³ Subjects who discontinue treatment early will be requested to return for an early discontinuation (ED) visit to complete all Visit 5 assessments and to return for a follow-up (FU) visit 14 ± 3 days after last IP administration.

EVENT	SCREENING PERIOD	TREATMENT PERIOD ^{1,2}						FOLLOW-UP PERIOD ²
		1	2	3	4	5	ED ³	
Study visit	S	1						FU Visit
Study Weeks		Baseline	1	2	4	6		
Study Day (D) ± Days	-21 to -1	1	8 ± 2	15 ± 2	29 ± 2	43 ± 2	Early treatment discontinuation	57 ± 3
Pregnancy test ⁴	✓	✓			✓	✓	✓	
Physical examination	✓	✓				✓	✓	✓
Vital signs	✓	✓		✓	✓	✓	✓	✓
Body weight and height ⁵	✓	✓		✓	✓	✓	✓	✓
12-lead triplicate ECG	✓	✓		✓	✓	✓	✓	✓
Serology	✓							
QuantiFERON-TB Gold test	✓							
SARS-CoV-2 RT-PCR test ⁶	✓	✓	As needed					
SARS-CoV-2 serology test ⁶		✓	As needed					
Randomization		✓						
Clinical safety blood samples	✓	✓ ⁷		✓ ⁷	✓	✓ ⁷	✓	✓

⁴ Serum beta human chorionic gonadotropin at screening, baseline (Visit 1), Visit 4 and Visit 5, or at the ED visit, if applicable (all female subjects).

⁵ Height only to be measured at screening.

⁶ RT-PCR from a nasal swab sample at screening and RT-PCR from a nasal swab sample and serology testing at baseline (Visit 1), and as needed when subject presents signs and symptoms of SARS-CoV-2 infection.

⁷ Fasted glucose, fasted insulin and HOMA-IR only at Visit 1, 3 and 5 and the ED visit, if applicable.

EVENT	SCREENING PERIOD	TREATMENT PERIOD ^{1,2}						FOLLOW-UP PERIOD ²

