6.2.2. Primary Efficacy Parameter

The primary endpoint for this study is the change from baseline in DAS28 (CRP) at Week 6. The DAS28 (CRP) is a derived measurement with differential weighting given to each component such as TJC28, SJC28, patient's global assessment of disease activity (0–100-mm VAS), and serum CRP level. A DAS28-CRP below the value of 2.6 is interpreted as Remission.

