6.2.2.1. Derivation Rules

The DAS assessment is a derived measurement with differential weighting given to each component. The DAS28 (CRP) will be calculated at each assessment time point.

The components of the DAS28 arthritis assessment include:

- Tender Joint Count 28 (TJC28) ranges from 0-28
- Swollen Joint Count 28 (SJC28) ranges from 0-28
- High sensitivity C-reactive protein (hsCRP) (in mg/L)
- Patient's disease activity VAS (in mm) (ranges from 0 = best to 100 = worst)

The DAS28 (CRP) score will be calculated using the below formula:

$$\text{DAS28 (CRP)} = 0.56 \times \sqrt{\text{TJC28}} + 0.28 \times \sqrt{\text{SJC28}} + 0.36 \times \text{Ln}[1+\text{CRP}(\text{in mg/L})] + 0.014 \times \text{patient's disease activity VAS} (\text{in mm}) + 0.96 \text{ (Mack, Hsia, \& Aletaha, 2017)}$$

where Ln is the natural logarithm

A lower score is considered as better disease activity. If one of the component is missing at a specific analysis visit, DAS28 (CRP) will not be calculated for that assessment and will be set to missing.

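### No readable text masks post-baseline hsCRP, a DAS28(CRP) component, from sites, so Week 2 and Week 4 results could carry over into later joint counts; masking it would be a cheap improvement

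*Protocol*

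**What the plan says.** **hsCRP as a safety test.** Protocol 8.5.2 ends its clinical chemistry list with "low-density lipoprotein (LDL), and hsCRP". On results it says: "Clinical laboratory values outside the normal range will be flagged and clinical relevance will be assessed by the investigator". It makes no exception for hsCRP. The Schedule of Activities (Protocol 8.11) ticks safety bloods at screening, Day 1, Weeks 2, 4 and 6, early discontinuation and follow-up. The one footnote restricting which chemistry tests are done at which visit covers other analytes: "Fasted glucose, fasted insulin and HOMA-IR only at Visit 1, 3 and 5 and the ED visit, if applicable".

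**hsCRP as efficacy.** SAP 6.2.2 describes DAS28(CRP) as built from "TJC28, SJC28, patient's global assessment of disease activity (0–100-mm VAS), and serum CRP level", and SAP 6.2.2.1 lists the component as "High sensitivity C-reactive protein (hsCRP) (in mg/L". SAP 6.3.2.1 takes hsCRP out of the laboratory safety outputs and places it with efficacy. Protocol 6.1, criterion 6 ("Screening serum high sensitivity CRP (hsCRP") requires a value above the upper limit of normal, 5.0 mg/L, at screening.

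**Blinding and assessors.** Protocol 6.5.2 says the subjects and the study team, including investigators, "clinical study coordinators, and sponsor personnel are blinded to treatment assignment"; it does not mention laboratory values. Protocol 8.4.1 says "A joint assessor with adequate training and experience in performing joint assessments will be designated at each study site". It asks for training and, as far as possible, the same assessor per subject, but not for separation from laboratory results. The opening of Protocol 8 asks that the person who made a subject's baseline determinations also complete the later safety and efficacy evaluations. Protocol 8.1 gives a preferred order within a visit: patient questionnaires, then investigator questionnaires and joint counts, with blood sampling last.

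**The concern.** Apart from hsCRP, the DAS28(CRP) components rest on judgement: tender joints, swollen joints and a patient scale. Protocol 5.3 expects the drug to reduce pro-inflammatory cytokines. If it lowers CRP, an assessor who has seen a subject's hsCRP fall may suspect active treatment and count fewer joints at the next visit. The change in hsCRP itself is a legitimate part of the score; the concern is a second, unintended contribution through the joint counts. It would favour the active arm, in a trial of 25 subjects whose result feeds a signal / no-signal rule.

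**Working it through.** **Step 1: which results can reach which assessments.** This assumes the preferred order in Protocol 8.1 is followed and that hsCRP is reported with the rest of the panel.

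| hsCRP sample | Same-visit joint count | Later joint counts open to influence |
|---|---|---|
| Week 2 | already done | Week 4, Week 6 |
| Week 4 | already done | Week 6 |
| Week 6 | already done | none |

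The Week 6 endpoint is therefore exposed only through the Week 2 and Week 4 results.

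**Step 2: the plan's own operating characteristics.** Inputs from Protocol 9.1 and SAP 6.2.2.3: SD 1.3, 15 + 10 subjects, TV -1.6, LRV -0.6; signal if P10 < TV and P80 < LRV.

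- SE = 1.3 × √(1/15 + 1/10) = 0.531.
- P10 < -1.6 requires an estimate below -1.6 + 1.282 × 0.531 = -0.920.
- P80 < -0.6 requires an estimate below -0.6 - 0.842 × 0.531 = -1.047, which is the binding limit.
- P(signal) at a true -1.6: Φ((-1.047 + 1.6)/0.531) = 0.851 (plan: 0.852).
- P(signal) at a true -0.6: Φ((-1.047 + 0.6)/0.531) = 0.200 (plan: 0.192). A t-based simulation gives 0.190.

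The stated figures reproduce, and this point does not affect them.

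**Step 3: what a small change in joint counts is worth.** The DAS28(CRP) weights are in SAP 6.2.2.1. The starting counts (12 tender, 10 swollen) and the one-joint shift are assumptions.

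- Tender: 0.56 × (√12 - √11) = 0.083.
- Swollen: 0.28 × (√10 - √9) = 0.045.
- Sum: 0.128, or 0.13 per affected subject.

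**Step 4: from subject to treatment contrast.** Bias = 0.128 × (proportion affected on active - proportion affected on placebo).

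- Equal proportions, for example because the drug does not alter CRP: 0.
- 60% against 20% (assumed): 0.128 × 0.4 = 0.05.
- 100% against 0% (the extreme): 0.13.

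**Step 5: effect on the decision rule at the extreme.** At a true -0.6 with a bias of 0.128 favouring active, P(signal) = Φ((-1.047 + 0.728)/0.531) = Φ(-0.60) = 0.27, against 0.20 without bias. This is an upper case under the one-joint assumption, not a forecast.

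**Step 6: would masking disturb another rule?** In the readable text, hsCRP and DAS28 are used for eligibility at screening only. The discontinuation rules in Protocol 6.4 do not use CRP, and SAP Appendix I has no CRP grade.

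**The case against.** The strongest reply is that the route is inferred. No sentence says hsCRP results go to sites. The inference joins hsCRP's place in the panel to a general sentence about flagged values. The laboratory manual is a separate document, and parts of the efficacy and timing sections are blacked out, so masking might be specified there. This stands as a limit on certainty. However, the blinding section is readable and is where such a provision would be expected.

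Second, CRP may be a weak cue to treatment. Criterion 6 applies at screening, up to 21 days before dosing, so some subjects may be in range by Day 1. Selection on a high value would also be expected to produce falls in both arms through regression to the mean. This stands, and it pulls the contrast bias toward the lower end of the range.

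Third, the preferred order of assessments is a real partial safeguard. It removes same-visit influence but not carry-over.

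Fourth, the protocol names infection as a risk and calls for careful monitoring (Protocol 5.5), so withholding a listed safety test has a price. This stands too, and the fix has to provide for it.

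A reader might also infer that normalisation is flagged to the investigator by Week 2, or that patients who know their CRP would score their global assessment differently. The documents support neither. Only out-of-range values are flagged, the first post-baseline sample is drawn at the Week 2 visit itself, and nothing says subjects receive laboratory results. Any effect on the patient global would be indirect and is undocumented.

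**Conclusion.** The point holds as a cheap improvement, not as a demonstrated bias. As written, an endpoint component that the SAP treats as efficacy sits in a panel reviewed by the investigator. No readable text masks it, and Protocol 8 encourages continuity of the person doing safety and efficacy evaluations rather than their separation. The exposure is carry-over from the Week 2 and Week 4 results to the Week 4 and Week 6 joint counts.

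The size cannot be estimated, because the documents do not give the drug's effect on CRP or how assessors would respond. Under the assumed one-joint shift the contrast bias is between 0 and 0.13, and nil if the drug does not alter CRP. It would be tempting to compare 0.13 directly with the LRV of -0.6. The documents do not support that: the LRV is a between-arm difference, and 0.13 becomes one only if every active subject and no placebo subject is affected. Nor do they support saying that the blind fails; treatment assignment itself remains protected.

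**What to change.** In Protocol 8.5.2 and 6.5.2, state that:

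- the central laboratory withholds post-baseline hsCRP from site reports and from reports to the blinded sponsor team until database lock;
- the unblinded safety committee (Protocol 10.1) can still see the values;
- the sponsor defines a separate route for releasing an hsCRP value to the site for safety reasons.

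The third item is needed because the laboratory alerts planned in Protocol 5.5 start at Grade 3 and SAP Appendix I does not grade CRP, so they would not cover it. The release criterion is for the sponsor to set. If the laboratory manual already masks hsCRP, a sentence in the protocol saying so is enough.

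The cost is a change to the laboratory report configuration, short protocol text in two sections, and the work of defining the release route. The downside is that sites lose routine hsCRP as an infection cue unless it is released; white cells and the other tests stay visible.

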2.1.5. Embryo-fetal Development Toxicity

The safety of GLPG3970 for use during pregnancy has not been established.

[REDACTED]

[REDACTED]

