6.3.1.1. Female Subjects

Female subjects are considered of non-childbearing potential if they meet one of the following criteria:

- No menses for 12 or more months without an alternative medical cause. A high follicle stimulating hormone (FSH) level in the postmenopausal range may be used to confirm a postmenopausal state in women not using hormonal contraception or hormonal replacement therapy. However in the absence of 12 months of amenorrhea, a single FSH measurement is insufficient.
- Permanently surgically sterile (bilateral oophorectomy, i.e. surgical removal of ovaries, bilateral salpingectomy or hysterectomy, i.e. surgical removal of uterus).

All other female subjects are considered to be of childbearing potential (WOCBP) and must use one of the following highly effective methods of birth control prior to the first dose of IP, during the clinical study and for at least 35 days after the last dose of IP:

- Combined (estrogen and progesterone containing) (oral, intravaginal, transdermal) hormonal contraception associated with inhibition of ovulation plus a barrier method.
- Progesterone-only hormonal (oral, injectable, implantable) contraception associated with inhibition of ovulation plus a barrier method.
- Intrauterine device.
- Intrauterine hormone-releasing system plus a barrier method.
- Bilateral tubal occlusion.
- Sexual abstinence defined as refraining from heterosexual intercourse during the entire period of risk associated with the study treatments. The reliability of sexual abstinence needs to be evaluated in relation to the duration of the clinical study and the preferred and usual lifestyle of the subject.

Periodic abstinence (e.g. calendar, symptothermal, post-ovulation methods), declaration of abstinence for the duration of a clinical study, withdrawal, spermicides only, and lactational amenorrhea method are not acceptable as methods of contraception.

In case a WOCBP has a vasectomized partner, provided that partner is the sole sexual partner of the WOCBP clinical study participant and that the vasectomized partner has received medical assessment of the surgical success, then she is not required to use an additional form of contraception.

Within these limits, the specific forms of contraception employed are left to the discretion of the subject, the investigator, and/or the subject's physician.

The safety of GLPG3970 during breastfeeding is unknown. Nursing women are not allowed to take part in this clinical study.

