7.2. Dosage and Administration

GLPG3970 will be provided as a powder and solvent to be reconstituted by the subject prior to use. The final dosage form for administration is an oral solution containing 400 mg of the active pharmaceutical ingredient G1567970 (G1567970 is the compound code for GLPG3970). A placebo powder and solvent for oral solution, to be reconstituted prior to use, will be also provided.

The IP needs to be taken q.d. at approximately the same time every morning on an empty stomach (i.e. IP intake should be at least 1 hour prior and at least 2 hours after a meal). At the baseline visit (Visit 1), IP will be administered on site after predose assessments have been completed. On visits 3, 4, and 5 subjects also need to take their IP on site. At Visit 1, 3, 5, and if applicable the ED visit, subjects need to come for the study visits in a fasting state (no food intake for at least 8 hours).

Subjects will receive powder and solvent to take home. The total content of the oral solution, reconstituted from the whole amount of powder and solvent, will need to be drunk. Detailed instructions for preparing and storing the applicable doses will be provided to the subject via on-site training on dummy kits and via a patient leaflet.

If a subject misses a dose (e.g. because he/she forgot to take the medication), he/she should take the missed dose within 12 hours after the planned intake time. If IP is not taken within 12 hours after the planned time, the missed dose should be skipped. For each dose taken at home, the time and date should be recorded in the subject's diary.

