2.5. Scheduled of Assessments

The study assessments will be undertaken at time points as specified in the Schedule of Assessments (Table 1). For detailed instructions on the clinical study procedures, please see the relevant CSP sections and CSP Section 8.1, “Timing of Assessments”.

Table 1 Schedule of Assessments

EVENT	SCREENING PERIOD	TREATMENT PERIOD ^{1,2}						FOLLOW-UP PERIOD ²
		1	2	3	4	5	ED ³	
Study visit	S	1						FU Visit
Study Weeks		Baseline	1	2	4	6		
Study Day (D) ± Days	-21 to -1	1	8 ± 2	15 ± 2	29 ± 2	43 ± 2	Early treatment discontinuation	57 ± 3
On site visit	✓	✓		✓	✓	✓	✓	✓
Telephone call			✓					
Informed consent	✓							
Inclusion/exclusion criteria	✓	✓						
Demographics	✓							
Medical history	✓							
FSH test (postmenopausal women)	✓							
Pregnancy test ⁴	✓	✓			✓	✓	✓	
Physical examination	✓	✓				✓	✓	✓

¹ On dosing days, all assessments are to be performed within 3 hours pre-dose, unless otherwise specified.

² Subjects must come for the study visits 1, 3 and 5 in the morning in a fasting state (no food intake for at least 8 hours). For Visit 1 (predose measurements) and for 2 post dose visits (Visit 3, 4 or 5) all attempts should be made to plan the visit within 2 days following MTX intake.

³ Subjects who discontinue treatment early will be requested to return for an early discontinuation (ED) visit to complete all Visit 5 assessments and to return for a follow-up (FU) visit 14 ± 3 days after last IP administration.

⁴ Serum beta human chorionic gonadotropin at screening, baseline (Visit 1), Visit 4 and Visit 5, or at the ED visit, if applicable (all female subjects).

EVENT	SCREENING PERIOD	TREATMENT PERIOD ^{1,2}						FOLLOW-UP PERIOD ²
		1	2	3	4	5	ED ³	
Study visit	S	1						FU Visit
Study Weeks		Baseline	1	2	4	6		
Study Day (D) ± Days	-21 to -1	1	8 ± 2	15 ± 2	29 ± 2	43 ± 2	Early treatment discontinuation	57 ± 3
Vital signs	✓	✓		✓	✓	✓	✓	✓
Body weight and height ⁵	✓	✓		✓	✓	✓	✓	✓
12-lead triplicate ECG	✓	✓		✓	✓	✓	✓	✓
Serology	✓							
QuantiFERON-TB Gold test	✓							
SARS-CoV-2 RT-PCR test ⁶	✓	✓					As needed	
SARS-CoV-2 serology test ⁶		✓					As needed	
Randomization		✓						
Clinical safety blood samples	✓	✓ ⁷		✓ ⁷	✓	✓ ⁷	✓	✓
Clinical safety urine samples ⁸	✓	✓ ⁹		✓	✓	✓ ⁹	✓	✓

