6.3.2.9. Presentation of Results

No formal inferential statistics (p-values) will be derived.

Continuous laboratory tests¹⁶ including glucose, cholesterol, triglycerides, low-density lipoprotein (LDL), high-density lipoprotein (HDL) and fasted glucose, will be summarized by means of descriptive statistics (including 90% CI of the mean change) by laboratory test, treatment group and analysis window. Actual values, changes from baseline and percent change from baseline will be tabulated separately. Continuous values for metabolic markers will be summarized in the pharmacodynamic analysis section.

Profile line plots by subject of all actual observed values using relative day (ADY) will be presented by treatment group. Graphs of the mean (+- SE) actual values over time and of the mean (+- SE) change from baseline, and percent changes from baseline will be presented for all continuous laboratory parameters, with the exception of the metabolic markers. Also, line plots for subjects will be provided by treatment group.

The analysis of abnormalities will focus on assessments reported during the treatment period. Results reported before baseline will only be listed.

Non-graded abnormalities and toxicities grades of the actual values will be presented as shift tables of the worst-case abnormality/toxicity grade versus the baseline abnormality/toxicity

¹⁶ With the exception of the metabolic markers [fasted insulin, homeostatic model assessment of insulin resistance (HOMA-IR) and HbA1c] and inflammation marker hsCRP.

grade. The table will be created per laboratory test, treatment group and analysis period. The results of non-graded abnormalities and toxicities grades will be shown separately.

A frequency table of the number (percent) of subjects with treatment-emergent worst-case abnormalities/toxicity grade per laboratory test, treatment group and analysis period will be presented. The results of non-graded abnormalities and toxicities grades will be shown separately.

A frequency table of the number (percent) of subjects will be also provided for hepatotoxicity flags defined before. These abnormalities will be also flagged in the individual data laboratory listing.

Listing will be provided for the laboratory test along with flag for abnormality results. In addition, pregnancy result will be listed separately.

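### No pregnancy test is scheduled after Visit 5 for completers, so conceptions late in dosing (the last 7 to 14 days, on an assumed hCG detection lag) escape every scheduled test

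*Protocol*

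**What the plan says.** Protocol section 8.5.2 sets the pregnancy tests as "serum beta human chorionic gonadotropin at screening, baseline (Visit 1), at Visit 4 (Day 29) and at Visit 5 (Day 43", or at the ED visit where one takes place. The SAP schedule (section 2.5, footnote 4) lists the same visits: "Serum beta human chorionic gonadotropin at screening, baseline (Visit 1), Visit 4 and Visit 5, or at the ED visit, if applicable". The FU cell of the pregnancy-test row is empty in both schedules, while the row for safety blood samples is ticked at FU (Day 57 ± 3).

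The order of events at Visit 5 follows from two other statements. Footnote 1 of the protocol schedule (section 8.11) says: "On dosing days, all assessments are to be performed within 3 hours pre-dose, unless otherwise specified". No exception is made for the pregnancy test. Section 7.2 adds: "On visits 3, 4, and 5 subjects also need to take their IP on site". Subjects who stop early have the ED visit and are then asked "to return for a follow-up (FU) visit 14 ± 3 days after last IP administration".

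On risk, section 2.1.5 states: "The safety of GLPG3970 for use during pregnancy has not been established". The remainder of that section is redacted. Section 6.3.1.1 requires women of childbearing potential to use contraception "during the clinical study and for at least 35 days after the last dose of IP". Section 11.3.3 requires pregnancies to be reported within 24 hours and followed to delivery or interruption. For reporting, SAP section 6.3.2.9 says: "In addition, pregnancy result will be listed separately".

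**The concern.** For a woman who completes treatment, the last scheduled test and the last dose fall on the same day. Serum hCG becomes detectable only some days after conception, so a conception late in dosing gives a negative result at Visit 5 and is never tested for again on schedule.

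At stake is the detection of an exposed pregnancy. The duties to report and follow a pregnancy begin only once somebody knows of it. FU is the last planned contact: adverse event collection ends there (sections 8.5.1 and 11.3.1), and investigators need not actively seek serious events afterwards (section 11.3.2). Routine safety samples are destroyed after analysis (section 8.9), so the FU blood cannot be tested later. Without a scheduled test, detection depends on questioning at FU, on clinical suspicion leading to an unscheduled test, or on the woman's own later report.

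**Working it through.** The plan gives no figure to reproduce; the check is date arithmetic on the schedule.

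**Inputs from the documents**
- Last scheduled test for completers: Visit 5, Day 43 ± 2, before the dose (protocol 8.5.2; 8.11 footnotes 1 and 4).
- Last dose for completers: the same day, on site (7.2), so nominally 43 dosing days.
- FU visit: Day 57 ± 3, or 14 ± 3 days after the last dose for early discontinuers (8.11).
- Contraception after the last dose: at least 35 days, that is Days 44-78 at nominal timing (43 + 35 = 78).

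**Assumed input**
- L, the lag from conception to detectable serum hCG: 7 to 14 days. The documents do not give it.

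**Current plan.** The latest conception that the Visit 5 test can show is on Day 43 − L, so the last L dosing days are uncovered.
- L = 7: 43 − 7 = Day 36. Days 37-43 are missed: 7/43 = 16%.
- L = 14: 43 − 14 = Day 29. Days 30-43 are missed: 14/43 = 33%.

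Because test and last dose share a day, moving Visit 5 within Days 41-45 shifts the dates but leaves L days uncovered. The gap exists for any lag above zero.

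**With hCG at FU.** The latest conception that can be shown is on FU day − L.
- Nominal FU: 57 − 14 = Day 43 and 57 − 7 = Day 50. No dosing day is uncovered, and 0 to 7 of the 35 post-dose days are reached.
- Across the FU window: from 54 − 14 = Day 40 to 60 − 7 = Day 53.
- Worst combination of windows (Visit 5 on Day 45, FU on Day 54, L = 14): 45 − 40 = 5 dosing days remain uncovered.

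**Early discontinuers.** The ED test normally follows the last dose, but it has the same lag. FU comes 11 to 17 days after the last dose, so a test there reaches conceptions from 3 days before the last dose (11 − 14 = −3) to 10 days after it (17 − 7 = 10).

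| | L = 7 | L = 14 |
|---|---|---|
| Dosing days uncovered, current plan | 7 (16%) | 14 (33%) |
| Dosing days uncovered, FU test at Day 57 | 0 | 0 |
| Post-dose days reached by FU test at Day 57, of 35 | 7 | 0 |

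**The case against.** The strongest reply is that contraception, not testing, is the plan's main safeguard. Highly effective methods are required throughout and for at least 35 days after the last dose, with a barrier added to the hormonal methods. Other routes to detection also exist: an on-site FU visit with physical examination, open questioning about adverse events, a daily diary, permission for extra laboratory tests, and a pregnancy reporting duty with no end date. The plan already tests at baseline, mid-treatment and end of treatment, contains no contradiction here, and would expect very few cases among 25 subjects. How much a late conception matters depends on embryo-fetal and pharmacokinetic text that is redacted.

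Much of this stands. The expected number of cases is small, the hazard cannot be graded from the public text, and 16% to 33% is a share of calendar time, not of risk. It is also fair that taking the Visit 5 sample before the dose matters little in itself: a sample a few hours after the dose would have the same blind spot, because the gap comes from the lag. The FU test is only partial cover for the 35-day period.

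None of this closes the gap. Contraception lowers the number of pregnancies but does not detect one, and the plan itself judged testing during treatment worthwhile despite contraception. Unscheduled tests are permitted, not required, and an early pregnancy may prompt no suspicion. The reporting duty operates only on a pregnancy already known.

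**Conclusion.** The concern holds. The protocol text and both schedules agree that no pregnancy test is planned after Visit 5 for completers. On an assumed lag of 7 to 14 days, conceptions in the last 7 to 14 of 43 dosing days escape every scheduled test. The length of the gap rests on that assumption; its existence does not.

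This is a design choice that should be improved, not an inconsistency. It does not touch the primary efficacy analysis or the sample size. The case rests on low cost set against a real gap in safety surveillance: a test would not prevent exposure, but it would bring detection, reporting and follow-up forward.

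**What to change.** In protocol section 8.5.2 and the section 8.11 schedule (tick and footnote 4), add serum hCG at the FU visit for all female subjects, including those who discontinued early, run on the safety blood already collected there. Make the same change in the SAP section 2.5 schedule. The listing sentence in SAP section 6.3.2.9 is not limited to particular visits, so it is enough to make sure the FU result is included. Section 11.3.3 needs no change.

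Describe the test as covering conceptions up to about the last dose, not the whole 35-day contraception period.

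The cost is one central-laboratory assay per female subject and a protocol amendment submitted to the ethics committees. No extra visit is needed. No extra draw is expected, provided the FU sample volume is sufficient; that should be checked against the laboratory manual, which is a separate document.
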